4.4 Pre-Medications

To mitigate infusion-related reactions, premedication with an antihistamine and with acetaminophen, per institutional standards, is mandatory prior to each dose of avelumab.

Management of infusion-related reactions should follow guidelines set forth in Section 4.3.2.

4.5 Permitted concomitant therapy

Concomitant medication also includes all prescription, over-the-counter (OTC), herbal supplements, blood transfusions, and IV medications. The patient needs to notify the investigational site about any new medications he/she takes after the start of the study drug.

All concomitant medications received within 7 days before the first dose of trial treatment and 28 days after the last dose of trial treatment should be recorded in the patient's medical record.

4.6 **Prohibited concomitant therapy**

Patients are prohibited from receiving the following therapies during the Screening and Treatment Phase (including retreatment for post-complete response relapse) of this trial:

- Antineoplastic systemic chemotherapy or biological therapy.
- Immunotherapy not specified in this protocol.
- Chemotherapy not specified in this protocol.
- Investigational agents other than avelumab.
- Radiation therapy.
 - Note: Radiation therapy to a symptomatic lesion or to the brain may be allowed at the investigator's discretion.
- Live vaccines within 30 days prior to the first dose of trial treatment and while participating in the trial. Examples of live vaccines include, but are not limited to, the following: measles, mumps, rubella, varicella/zoster, yellow fever, rabies, BCG, and typhoid vaccine.
- Systemic glucocorticoids for any purpose other than to modulate symptoms from an adverse event of suspected immunologic etiology.

Patients who, in the assessment by the investigator, require the use of any of the aforementioned treatments for clinical management should be removed from the treatment portion of the study. Patients may receive other medications that the investigator deems to be medically necessary.

The Exclusion Criteria describes other medications which are prohibited in this trial.

4.7 Other Considerations

4.7.1 Contraception

Non-pregnant, non-breast-feeding women may be enrolled if they are willing to use 2 methods of birth control or are considered highly unlikely to conceive. Highly unlikely to conceive is defined as 1) surgically sterilized, or 2) postmenopausal (a woman who is \geq 45 years of age and has not had menses for greater than 1 year will be considered postmenopausal), or 3) not heterosexually active for the duration of the study. The two birth control methods can be 2 barrier methods or a barrier method plus a hormonal method to prevent pregnancy. Patients should start using birth control from study Visit 1 throughout the study period up to 120 days after the last dose of study drug.

The following are considered adequate barrier methods of contraception: diaphragm, condom (by the partner), copper intrauterine device, sponge, or spermicide. Appropriate hormonal contraceptives will include any registered and marketed contraceptive agent that contains an estrogen and/or a progestational agent (including oral, subcutaneous, intrauterine, or intramuscular agents).

Patients should be informed that taking the study medication may involve unknown risks to the fetus (unborn baby) if pregnancy were to occur during the study. To participate in the study they must adhere to the contraception requirement (described above) for the duration of the study and during the follow-up period as defined above. If there is any question that a patient will not reliably comply with the requirements for contraception, that patient should not be entered into the study.

4.7.2 Pregnancy and Lactation

Pregnancy

Pregnancy must be excluded before the initiation of and during avelumab therapy, and prevented by the use of reliable contraception during treatment.

If a patient inadvertently becomes pregnant while on treatment with avelumab, the patient will immediately be removed from the study. The site will contact the patient at least monthly and document the patient's status until the pregnancy has been completed or terminated. The outcome of the pregnancy will be reported to the Study Chair and to Pfizer without delay and within 24 hours to the Study Chair and within 2 working days to Pfizer if the outcome is a serious adverse experience (e.g., death, abortion, congenital anomaly, or other disabling or life-threatening complication to the mother or newborn).

The study investigator will make every effort to obtain permission to follow the outcome of the pregnancy and report the condition of the fetus or newborn to the Study Chair. If a male patient impregnates his female partner the study personnel at the site must be informed immediately and the pregnancy reported to the Study Chair and to Pfizer and followed as described above.

Lactation

It is unknown if avelumab is secreted in breast milk. Breast-feeding must be discontinued during treatment with avelumab.

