- 4. TSH monitoring will occur at baseline, cycle 2, cycle 4, then every 3 cycles thereafter (ie. Cycle 7,10 etc.), and at the end of treatment. For patients with asymptomatic TSH elevation, please refer to Section 4.3.1 for further evaluation. Specifically, if TSH < 0.5 x LLN, or TSH > 2 x ULN, or consistently out of range in 2 subsequent measurements: include T4 at subsequent cycles as clinically indicated; consider endocrinology consult.
- 5. Pregnancy test for females of child-bearing potential only.
- 6. Urinalysis (dipstick) will be performed at baseline, every 3 cycles following initiation of treatment (ie. Cycle 4, 7 and 10 etc.), and at the end of treatment. Urine microscopic examination should be performed if dipstick is abnormal.
- 7. EBV DNA plasma levels will be measured at baseline, every 3 cycles following initiation of treatment (ie. Cycle 4, 7, 10 etc.), and at end of treatment.
- 8. Newly obtained tumor tissue collection is mandatory upon study entry: See Section 5.5 for specifications. The study chair may grant exceptions to the mandatory biopsy should the treating physician deem that a biopsy is not feasible or unsafe for the patient, and archival tissue is available and provided for study purposes. A conversation with the study chair is required to obtain an exception. At time of disease progression, a repeat biopsy is encouraged but optional.
- 9. Blood for correlative studies should be collected at the same time blood is drawn for CBC and CMP if possible. 30 ml blood to be collected at baseline, at 12 weeks after treatment initiation (± 7 days). See Section 5.5.
- Imaging for radiographic disease assessment will be performed every 12 weeks following treatment initiation (± 7 days). The same imaging modality should be used throughout the study when feasible. For patients who are clinically stable, a repeat scan will be required 4 weeks (±7 days) after initial radiographic findings of disease progression as a confirmatory assessment. For CT or MRI, neck and chest should be evaluated; abdomen/pelvis as indicated. If a PET/CT is utilized, CT must be diagnostic quality.

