- 9. Female patient of childbearing potential has a negative serum or urine pregnancy within 72 hours prior to receiving the first dose of study medication.
- 10. Female patient of childbearing potential agrees to use 2 methods of birth control or be surgically sterile, or abstain from heterosexual activity for the course of the study through 120 days after the last dose of study medication (Reference Section 4.6.2).

Note: Females of childbearing potential are those who have not been surgically sterilized or have not been free from menses for > 1 year.

11. Male patient with a partner of childbearing potential agrees to use an adequate method of contraception starting with the first dose of study therapy through 120 days after the last dose of study therapy.

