4.0 TREATMENT PLAN

4.1 Study Design

This is a prospective, multi-center, open-label, single-arm phase II trial to evaluate the efficacy of Avelumab for patients with recurrent/metastatic, EBV-related nasopharyngeal carcinoma. A total of 39 patients will be eligible to enroll. Patients will be enrolled at 7 sites: UC San Diego Moores Cancer Center, Stanford Cancer Institute, UC Los Angeles Jonsson Comprehensive Cancer Center, UC Irvine Chao Cancer Center, University of Southern California Norris Comprehensive Cancer Center, Providence Cancer Center, and Dana-Farber Cancer Institute.

All patients providing informed consent will be screened for eligibility. Baseline assessments will include vital signs, physical exam, ECOG performance status evaluation, blood hematology and chemistries, urinalysis and tumor imaging. Upon study entry, all patients will receive Avelumab 10mg/kg IV on days 1 and 15 of each 28-day cycle. Treatment will be given until disease progression, unacceptable toxicity, investigator decision or patient withdrawal. Dose reductions and/or interruptions may occur per pre-specified criteria for grade 3 or higher toxicity.

History and physical examination, adverse event assessment and routine bloodwork will be performed prior to every cycle. For patients with known hepatic metastases at time of study entry, liver function tests (including ALT, AST, total bilirubin, and alkaline phosphatase) must be performed once weekly for 7 weeks upon treatment initiation. All patients will undergo imaging (CT, MRI, or PET/CT [CT must be diagnostic quality]) within 4 weeks prior to study entry, 12 weeks after treatment initiation (+/- 7 days), and then every 12 weeks thereafter (+/-7 days). Response will be assessed using RECIST. For patients who are clinically stable, a repeat scan will be required 4 weeks (+/- 7 days) after initial radiographic findings of disease progression as a confirmatory assessment.

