4.8 Patient Withdrawal/Discontinuation from Study Treatment

In the absence of treatment delays due to adverse events, study treatment may continue until:

- Disease progression
- The patient experiences unacceptable adverse event(s) or those events listed in the dose modification guidelines that require discontinuation;
- The patient exhibits an inter-current illness that prevents further administration of study

treatment,

- The patient has a confirmed positive serum pregnancy test;
- The patient or legal representative withdraws consent;
- The patient is noncompliant with trial treatment or procedure requirements;
- The patient is lost to follow-up;
- The patient dies;
- General or specific changes in the patient's condition render the patient unacceptable for further treatment in the judgment of the investigator;
- Administrative reasons.

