Baseline assessment of subject status for determining adverse events. See Section 7 for Adverse Event monitoring and reporting.

i. Laboratory Assessments

Laboratory tests for hematology, chemistry, urinalysis, and others are specified in Table 5-1.

Table 5-1. Laboratory tests

Hematology	Complete Blood Count (CBC) with differential
	o hemoglobin,

	 hematocrit,
	 platelet count,
	 white blood cell count,
	 percentage or absolute differential count
Chemistry	Comprehensive metabolic panel (CMP)
	o albumin
	 alkaline phosphatase
	 aspartate aminotransferase (ALT)
	 alanine aminotransferase (AST)
	 bicarbonate (CO₂)
	 blood urea nitrogen (BUN)
	o calcium
	o chloride
	o creatinine
	∘ glucose
	 potassium
	o sodium
	 total protein
	 total bilirubin
	Thyroid stimulating hormone (TSH)
Pregnancy Test	Urine human chorionic gonadotropin (HCG) or serum βHCG
Urinalysis	o Blood,
-	o Glucose,
	o Protein,
	 Specific gravity
	 Microscopic exam (if abnormal)
If clinically	Hepatitis B: HepB sAg and/ or Hep B DNA
indicated	Hepatitis C: Hep C RNA PCR
	HIV
	••••

j. Blood collection for correlative studies

See Section 5.5 for details.

k. Tumor assessment

Radiologic assessment is performed by MRI with gadolinium or CT with contrast (neck and chest; abdomen/pelvis as indicated) or PET/CT. If a PET/CT is performed, the CT must be of diagnostic quality. The same radiographic technique should be used throughout the study. However, a patient who develops a contraindication to undergo an MRI scan during study treatment may remain on study and undergo contrast enhanced CT scans.

I. Tumor biopsy and tissue collection

See Section 5.5 for details.

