5.2 Screening/Baseline Procedures

Assessments performed exclusively to determine eligibility for this study will be done only after obtaining informed consent. Assessments performed for clinical indications (not exclusively to determine study eligibility) may be used for baseline values even if the studies were done before informed consent was obtained.

All screening procedures must be performed within 21 days prior to registration unless otherwise stated. The screening procedures include:

- Written informed consent (within 28 days).
- Review of inclusion and exclusion criteria.

- Complete medical/oncology history.
- Demographics.
- Documentation of concomitant medications.
- Complete physical examination, including vital signs and height.
- Performance status assessment.
- Laboratory tests (within 7 days; pregnancy test within 72 hours).
- Blood collection for EBV DNA plasma levels and correlative studies.
- Documentation of tumor staging (imaging completed within 28 days).
- Tumor biopsy tissue collection for correlative studies (within 42 days).

5.3 **Procedures During Treatment**

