5.3.2 Each Additional Cycle, Day 1 (±3 days)

- Focused physical exam, including vital signs, ECOG performance status assessment and weight
- Assess for adverse events
- Update concomitant medications
- Collect blood samples for CBC with differential, CMP

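### Pregnancy must be excluded throughout avelumab therapy, but the only scheduled test is at screening, and the follow-up rule for female patients names only on-treatment pregnancy

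*Combined protocol and SAP*

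**What the plan says.** Section 4.7.2 sets the duty: "Pregnancy must be excluded before the initiation of and during avelumab therapy, and prevented by the use of reliable contraception during treatment". Section 4.8 lists among the reasons to stop treatment: "The patient has a confirmed positive serum pregnancy test".

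Testing is placed at one time only. Inclusion criterion 9 (Section 3.1) requires that a woman of childbearing potential "has a negative serum or urine pregnancy within 72 hours prior to receiving the first dose of study medication". Section 5.2 repeats the 72-hour limit, and the pregnancy row of the Schedule of Events has an entry only in the screening column. Footnote 5 of the Schedule says who is tested and nothing about repeats: "Pregnancy test for females of child-bearing potential only". Table 5-1 (Section 5.1) names the assay ("Urine human chorionic gonadotropin (HCG) or serum" beta-HCG) without a time point.

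For cycles after the first, the laboratory line in 5.3.2 reads "Collect blood samples for CBC with differential, CMP". The end-of-treatment list in 5.3.6 takes blood and urine but has no pregnancy test. Section 4.1 adds that "History and physical examination, adverse event assessment and routine bloodwork will be performed prior to every cycle".

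After treatment, 3.1 (criterion 10) and 4.7.1 require contraception for 120 days beyond the last dose. In 4.7.2, removal from study, monthly contact and outcome reporting for a female patient all hang on a sentence about conceiving while receiving avelumab. The clause on partners of male patients carries no time condition.

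**The concern.** Section 4.7.2 contains two duties, exclusion and prevention. The contraception rules serve the second. Nothing in the visit lists serves the first once dosing has begun, and the stopping rule in 4.8 depends on a test that no visit calls for. Treatment has no fixed end, so a site that follows the lists exactly would keep infusing through a pregnancy nobody suspects.

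The protocol itself treats fetal exposure as a risk. Section 4.7.1 has patients told of unknown fetal risk, and Section 1.3 reports very strong expression of the drug's target in placental tissue.

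The second gap follows treatment. The 120-day contraception period shows that the protocol regards those days as a time of risk. For a woman who conceives then, it is not explicit that the site must follow the pregnancy or report its outcome. Cover is clearer for the partner of a male patient than for the woman who received the drug.

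**Working it through.** The plan gives no figure of its own here, so the check compares the texts and counts days.

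**Is a repeat test scheduled anywhere?** Sections 5.3.1 to 5.3.6 list none. The Schedule footnotes for TSH, urinalysis and EBV DNA (4, 6 and 7) each state a repeat interval; footnote 5 does not. The Schedule row and the section text agree, so a table damaged in text extraction is an unlikely explanation. Scheduled tests after the first dose: 0.

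**Infusions without a scheduled test.** Dosing is on days 1 and 15 of each 28-day cycle, so infusion k falls on day 1 + 14(k − 1). Treatment duration is an assumption: 12 weeks is the first scheduled scan and is close to the median PFS of 11.4 to 11.9 weeks in the avelumab cohorts of Section 1.5 (other tumours); 24 weeks is about the 6-month endpoint.
- To day 84: k = 6 (last on day 71); after the first dose, 6 − 1 = 5.
- To day 168: k = 12 (last on day 155); after the first dose, 12 − 1 = 11.
- With a test on day 1 of each cycle, at most 2 infusions fall between tests.

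**Days after the last dose.**
- The end-of-treatment visit is at 28 ± 7 days, that is day 21 to 35, so 120 − 35 = 85 to 120 − 21 = 99 contraception days come after it.
- Non-serious events are recorded to day 28: 120 − 28 = 92 days lie outside.
- Serious events are recorded to day 90, or to new anti-cancer therapy if earlier (7.1): 120 − 90 = at least 30 days lie outside.
- Assume 36 to 40 weeks (252 to 280 days) from conception to term. Conception on days 1 to 120 then gives a birth from day 1 + 252 = 253 to day 120 + 280 = 400, which is 163 to 310 days after day 90.

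**What else covers those 120 days?**
- Section 7.3 lists congenital anomaly as a seriousness criterion, but not pregnancy.
- Section 7.6.3 covers serious events and a category of non-serious events of interest that is not defined.
- Section 7.6.4 has no end date. Its FDA rules and its first category of unanticipated problem need an event that is serious or life-threatening, not anticipated, and possibly related. Categories 4 (new findings that change risk against benefit) and 6 (complaints) need no serious event. An uncomplicated pregnancy would not automatically qualify under any of these.
- Sections 4.1 and 5.4 and the Schedule set contact every 3 months for all patients who stop treatment; 4.9 says every 3 to 6 months after progression. Under both 4.9 and 5.4 a survival contact may be a record review or an index check.
- A later paragraph of 4.7.2, on efforts to follow the outcome, does not repeat the on-treatment condition but can be read as referring back to it.

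**The case against.** The strongest reply is that 4.7.2 binds sites whatever the Schedule shows. It states the duty, Table 5-1 supplies the test without restricting when it is used, and the method on treatment is left to the site. On that view only an interval is missing. The protocol also has real safeguards: two contraceptive methods, exclusion criterion 16 (which bars anyone expecting to conceive during the trial), the 4.7.1 instruction not to enter a patient whose compliance with contraception is in doubt, and an assessment before every cycle that could prompt a test for cause. All of this stands and lowers the chance of an unsuspected pregnancy. It does not tell a site when to look for one.

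A reader might infer that the protocol permits dosing of a woman known to be pregnant, or prevents sites from testing. It does neither: 4.7.2 and 4.8 stop treatment, and unscheduled tests are open to sites.

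A reader might also infer that pregnancies after treatment fall wholly outside the reporting rules. That is too strong. Serious events are collected to day 90, 7.6.4 runs without limit, 3-monthly contact is specified for progressed patients too, and the outcome paragraph of 4.7.2 is ambiguous rather than silent. The cover is partial.

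Finally, patients may already be told to report a pregnancy in consent pages that are not part of the available text. The absence of such an instruction cannot be asserted.

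**Conclusion.** The point holds as an internal mismatch that should be corrected. The duty to exclude pregnancy during therapy has no scheduled means of being met, and the follow-up rule for female patients is explicitly narrower than the 120-day period in which contraception is required.

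Its size in patients cannot be stated. The documents give 39 patients in total and no number of women of childbearing potential or pregnancy rate. The counts of 5 and 11 infusions rest on assumed durations of 12 and 24 weeks. A reader might take them as a measure of harm, but they count infusions with no scheduled check, not infusions given during a pregnancy. The 163 to 310 days rest on the gestation assumption and show only that the serious-event window closes before any term birth from a conception after the last dose.

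This is a safety-procedure matter. The response endpoint, the two-stage design and the primary analysis are unaffected.

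**What to change.** 1. For women of childbearing potential, add a urine or serum HCG test to the Schedule of Events, 5.3.2 and 5.3.6: for example on day 1 of each cycle from cycle 2 and at the end-of-treatment visit, with serum confirmation of a positive result. The per-cycle interval is one reasonable choice.
2. In 4.7.2, apply the follow-up and outcome-reporting sentences to any pregnancy in a female patient that is detected after the first dose or conceived up to 120 days after the last dose, and follow it to outcome regardless of the 90-day serious-event window. This also covers a conception too early for the screening test to show. Keep immediate removal for on-treatment pregnancy and leave the partner clause as it is.

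A separate direct contact about 6 months after the last dose would help to detect late conceptions, but it is optional and not part of the required change.

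Cost per woman of childbearing potential, counting one test per cycle from cycle 2 plus one at end of treatment:
- 12 weeks (3 cycles): 2 + 1 = 3 tests
- 24 weeks (6 cycles): 5 + 1 = 6 tests
- 52 weeks (13 cycles): 12 + 1 = 13 tests

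All fall at visits where blood is already drawn. There will be an occasional false positive that needs serum confirmation, and a conception near day 120 will need dating. Under Section 10.8 the amendment goes to the IRBs of the 7 sites and to the FDA, possibly with a revised consent form; it can be bundled with another amendment.

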4.7.3 Overdose

Symptoms

Experience with overdose of avelumab is not available.

Management

Treatment is directed to symptoms.

4.8 Patient Withdrawal/Discontinuation from Study Treatment

In the absence of treatment delays due to adverse events, study treatment may continue until:

- Disease progression
- The patient experiences unacceptable adverse event(s) or those events listed in the dose modification guidelines that require discontinuation;
- The patient exhibits an inter-current illness that prevents further administration of study

treatment,

- The patient has a confirmed positive serum pregnancy test;
- The patient or legal representative withdraws consent;
- The patient is noncompliant with trial treatment or procedure requirements;
- The patient is lost to follow-up;
- The patient dies;
- General or specific changes in the patient's condition render the patient unacceptable for further treatment in the judgment of the investigator;
- Administrative reasons.

